3.6 Device safety - Compliance Pre-clinical

3.6.1 Compliance and Pre-Clinical

The pre-clinical testing that was performed on PregSense is described hereunder:

(1) Electrical Safety testing:

- EN 60601-1:2006/A1:2013 [EU harmonized version] & ANSI/AAMI ES60601-1:2005/(R) 2012 and A1:2012, C1:2009/(R) 2012 and A2:2010/(R) 2012 [FDA recognized version] Medical electrical equipment - General requirements for basic safety and essential performance.
- IEC 60601-1-11: 2010 /IEC 60601-1-11: 2015 Medical electrical equipment - General requirements for basic safety and essential performance - Collateral standard: Requirements for medical electrical equipment and medical electrical systems used in the home healthcare environment

(2) EMC:

- EN 60601-1-2: 2007 [EU harmonized version] & IEC 60601-1-2: 2007 [FDA recognized version] Medical electrical equipment - General requirements for basic safety and essential performance – Collateral standard: Electromagnetic compatibility - Requirements and tests (FDA also recognizes the 4th edition of this standard, IEC 60601-1-2: 2014.
- FCC CFR 47

(3) Biocompatibility testing:

Nuvo PregSense sensors are produced under ISO 13485 quality system. The sensors were tested for biocompatibility according to ISO 10993-1, ISO 10993-5 for:

- In-vitro cytotoxicity

(4) Batteries:

- UL 1642 5th edition for Lithium Batteries.
- IEC 62133: 2012 Secondary Cells and Batteries Containing Alkaline or Other Non-Acid Electrolytes - Safety Requirements For Portable Sealed Secondary Cells, And For Batteries Made From Them, For Use In Portable Applications.

(5) Tests performed by Nuvo Group:

- Each Software version of the system is verified according to the Software standards ISO 60601-1 section 14 and ISO 62304.
- FDA Guidance document – General principles of software Validation: Final Guidance for Industry and FDA Staff.
- Each system undergoes strict functionality testing before release according to written test procedures.

3.6.2 Previous Clinical evaluation

A study evaluating the Fetal Heart Rate (FHR) data recording for developing a continuous FHR monitoring using a designated sensory belt was conducted in Hadassah Hospital, Jerusalem, Israel. This study was conducted to assess the feasibility and safety of PregSense™.

During the feasibility study a total of 76 subjects participated for which a total of 510 recording sessions were executed. Female subjects aged ≥ 18 years and ≤ 50 years with singleton pregnancy between 20-40 weeks' gestation and who were capable of signing informed consent were included in the study.

PregSense™ was recorded simultaneously with the industry standard BIOPAC™ MP-150 biomedical data acquisition system. No adverse events, procedure-related or device-related, were reported during the study.

3.7 Risk Management analysis

Risk Analysis was performed according to the guidelines of the Risk Management Standard ISO 14971:2012 / ISO 14971:2007 Medical devices - Application of risk management to medical devices.

- All risk control measures have been implemented and verified. The overall residual risk for the device has been found to be acceptable using the criteria defined in the risk management plan.
- A review of the individual risks against the benefits of the device indicates that the benefits of the device outweigh the risks involved in all cases.

For further risk analysis information, please see the section 11.2 in the Investigator Brochure

4 STUDY ENPOINTS

4.1 Primary Performance Endpoints:

The primary performance endpoints will include:

- Fetal HR

Maternal HR Both endpoints will be collected via PregSense™ and via the standard of care monitoring system (CTG).

4.2 Safety endpoints:

Incidence of device related and/or protocol procedure related adverse events and/ or serious adverse events related to the study device, in pregnant women with singleton pregnancy > 24 + 0 weeks of gestation.

4.3 Secondary Performance Endpoints:

The secondary performance endpoints will include:

- Uterine contractions

PregSense™ also acquires and displays the UA (Uterine contractions) tracing from the uterine Electrohysterography (EHG) signal.

Contractions will be collected via PregSense™ and via the standard of care monitoring system (CTG).

5 STUDY DESIGN

5.1 Study Overview and plan

This study is a prospective, open label, comparative, multi-center study.

This study will be performed to collect and digitally record data from PregSense™, and the standard of care (CTG) in order to provide evidence of safety and agreement between PregSense™ and the standard of care devices (for further information see section 6.1.2, and 8.2).

During the study conduct, Nuvo Group will continuously review adverse events and will meet (as needed) periodically to review the accumulated safety data (for further information, see section 9).

5.1.1 Screening

An initial subject screening evaluation will be done during consultation or on the phone in order to identify eligible candidates. This will be applied on all trial subjects.

The candidate will then be invited to the first visit in which, confirmation of the eligibility criteria will be performed. All screened subjects will be identified by a subject number and will sign an Informed Consent Form (ICF) prior to any study procedure initiation. Each subject will receive a detailed explanation about the study purpose and procedure; at the end of the explanation, the

subject will sign an ICF. An authorized study personnel will take the subject's measurements and vital signs and will confirm that the subject meets the Inclusion/ Exclusion criteria.

Sites will make all efforts to maintain a balanced distribution of subjects across the different weeks of pregnancy. An attempt will be made to include at least 5 women with contractions in each site.

5.1.2 Recording session

The primary objective is to assess the agreement between the PregSense™ device data collection, and the values as measured via the standard of care used for prenatal monitoring (i.e. CTG).

First, the authorized study personnel will register the subject into the App. If the subject is already registered, the subject's study I.D number will be entered to the App.

PregSense™ WSB then will be applied by the authorized study personnel to the maternal abdominal area of the subject after cleaning the maternal abdomen with a damp cloth, then drying the abdomen. Before initiating the recording session, a valid signal should be obtained. Therefore, a 2 minutes signal validation test will be executed. If validation test fails, re-adjustment of the PregSense™ WSB connections and placement should be re-validated, then another validation test will follow (if validation test does not pass after three adjustments the subject shall be excluded).

Once the validation test has passed, a 10-minute session will be recorded.

After session completion, the authorized study personnel will apply the CTG transducers, and will confirm fetal heart rate detection according to the standard of care procedure.

If a valid signal is detected, a new 30-minute session will be initiated recording both systems simultaneously in a synchronized method (PregSense™ and CTG).

Following the completion of the sessions, the nurse/clinician will remove both monitoring systems from the maternal abdomen.

5.2 Early Discontinuation

Subjects are free to discontinue their participation in the study at any time and without prejudice to further treatment and without naming the reasons. It will not have any impact on their treatment.

5.2.1 Criteria for Early Discontinuation

Subjects who prematurely discontinue the study should be followed and treated by the investigator in a customary manner.

A subject may withdraw or be withdrawn from the study for the following reasons:

- Subject withdrew consent.
- Request of Sponsor to terminate the study.
- Request of primary care physician or investigator.
- Subject is non-compliant with study procedures.
- Protocol violation.
- Subject is unable to continue the study.
- Subject experiences an adverse event (whether considered related to the investigational product or not) that results in a medical condition that may prevent the subject from meeting study criteria.
- Death.

Reasons for premature withdrawal from the study must be stated in the CRF and in the site source documentation.

If there is more than one reason for early withdrawal from the study, all the reports should be stated.

The study may be stopped following an unexpected event, which does not permit continuation of the study. The Investigator and/or the Sponsor and/or local EC and/or regulatory authority/Competent Authorities can decide to terminate the study.

The data collected up until the withdrawal point will be valid and available for insertion into the study database and the development of the analysis.

5.2.2 Sponsor's Termination of Study

The Sponsor reserves the right to discontinue the study at any time for any reason. The Sponsor may also discontinue the study at a site due to poor performance or compliance. The investigator must implement the Sponsor's request to terminate the study in a time frame that fits best with the subjects' well-being.

6 SUBJECT ELIGIBILITY

6.1 Inclusion criteria:

The study population will consist of the following inclusion criteria:

1. Female age between: 18-50
2. Gestational age >32 + 0 weeks
3. Singleton pregnancy
4. Ability to understand and sign informed consent

6.2 Exclusion criteria

1. BMI ≥ 45 and $15 \leq$ prior pregnancy
2. Multiple gestation
3. Fetal Anomaly
4. Uncontrolled Hypertension
5. Subjects with skin problems in the abdominal area (such as; wounds, cuts in the skin, skin rash, etc.)
6. Subjects with implanted electronic devices (pacemakers, defibrillator, etc.)
7. Subjects who, in the judgment of the investigator, are likely to be non-compliant or uncooperative during the study

7 STUDY CONDUCT

7.1 Screening & Enrollment

The enrollment procedure will include:

- Assessment of eligibility to participate in the study.
- Informed Consent must be obtained prior to enrollment.
- The subject will undergo routine registration procedure and will be identified by a personal code in addition to their initials.
- The Case Report Form (CRF) will be filled by certified and trained clinician and/or authorized personnel, including recording of all relevant subject details (such as Weight, height, estimated Due date, concomitant medications, medical history, date of signature on the ICF, recording date and hour, problems detected during recordings, etc.).

7.1.1 Assessment of eligibility

Study authorized personnel will evaluate subjects' eligibility to participate in the study. All potential trial candidates will be screened for eligibility. Only subjects who meet all inclusion criteria and none of the exclusion criteria will be eligible for enrollment.

Eligibility to participate in the study will be ascertained by the investigator based on the inclusion and exclusion criteria.

Sites will make all efforts to enroll an equal number of the subjects across the different gestational age.

7.1.2 Informed Consent Process

The subject will be requested by the investigator to sign the ICF, according to the declaration of Helsinki and local regulations. The subject will receive a full oral explanation on the study and will receive a copy of the subject ICF and subject Information Form.

The consent to participate in this study must be given in writing. The signed informed consent will remain in the file of the subject; a signed copy will be given to the subject.

A subject identification log (LOG-CLI-04-04) will be kept at the site with all subjects signed ICF documentation for participating in the study. The log will include the subject's full name, ID number, initials, subject number and date of enrollment.

7.1.3 Subject identification code

Following the enrollment, each subject will be assigned a unique study number that will be used to identify results. The subject will receive an identification number of 10 digits.

The first digit will be the code of the country; "1" for Germany, "2" for USA etc.

The 2nd and 3th digits will be the code of the site; "01" for Heidelberg, "02" for Hadassah etc. the 5th, 6th and 7th digits will be the code of the protocol; "1000" for the Pivotal trial etc. The last 3 digits (8th to 10th digits) will be the code of the subject CRF number; "001", "002" etc.

The identity of all study participants will be kept strictly confidential.

7.2 Recording session

In general, the treatment of a subject enrolled to the study will be performed according to the medical and hospital guidelines. Each recording session will last at least 30 min as according to the standard of care.

Important Note: The physician or any other medical personnel are not allowed to make any medical decisions or treatments based on the information received from PregSense™.

7.2.1 Recording

The PregSense™ will be connected and operated in the most continuous manner as possible recording the fetal cardiac activities and maternal cardiac activities, unless there is a necessity to disconnect the subject due to medical treatment or nursing reasons.

The data will include the following:

- Fetal HR
- Maternal HR
- Uterine activity

The PregSense™ records will be identified by the subject's trial identification number.

7.2.2 CTG and data recording

The data from the CTG + Pulse Oximeter monitoring system will be recorded in real time by a dedicated SW system in parallel to the PregSense™.

A pulse Oximeter is used to monitor MHR with the CTG/NST device.

All data should be stored under the subject study ID number and will be analyzed offline.

7.2.3 Testing Set-up

Additional equipment to be used during the testing:

- CTG - Phillips Avalon FM30/FM20 + Pulse Oximeter with a dedicated PC and cable connections
- Ultra Sound Imaging if applicable

7.3 Standard of Care

During all study periods, subjects will receive Standard of Care in accordance to the general management of the site.

7.4 Concomitant tests, therapy and treatment

All concomitant medications/therapies administered during the study and may affect the data collected are to be recorded in the appropriate CRF page. There are no restrictions on the use of concomitant medications, as dictated by the study device.

Any investigational medication/therapy or off-label uses of drugs and devices are prohibited during the study.

7.5 End of study/Completion of study

Completion of study will be defined by the subject compliance, thus, subjects who finished the study without protocol violations and had at least 1 minute of data where a signal was recorded and detected with both devices at the same time.

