Medical Device Description:	
PregSense™, developed and designed by Nuvo Group, consists of the following three basic components:
 
 (1) Wearable device – containing; 
 a. The sensors module (WSB- Wearable Sensory Belt) b. The major electronic module (WSH - Wireless Sensing Hub) (2) Mobile Application (MA) – 
 a. Gateway Service Application b. Presentation Application: 
 i. MD Application: ii. ME Application: (3) Cloud based application 
PregSense™ will include the following features [Please note, in PregSense Apps (ME, MD or Pivotal Study App) the features might be presented in alignment with the end user requirements]:
 
 • FHR (Fetal Heart Rate) • MHR (Maternal Heart Rate) • Fetal heart rate response (Fetal Activity) (in PregSense ME App) • Maternal Activity (in PregSense ME App) • Uterine Activity (Uterine Contractions, if applicable) 
Note: For this Pivotal study, a subversion of the Application with study metrics only will be applied, in order to show the agreement between PregSense and the standard of care device (i.e. CTG).

Study Endpoints:	
Primary Performance Endpoints:
 
 • Fetal HR

**CLINICAL STUDY EVALUATING THE SAFETY OF THE NON-INVASIVE
PRESENSE™ AND COMPARATIVE PERFORMANCE OF PRESENSE™
VERSUS CTG INPRENATAL MONITORING OF PREGNANT SUBJECTS**

Ref. No.: CLP1000

Rev. 05

Page 10 of 42

- Maternal HR

Safety Endpoints:

- Safety, tolerability and compliance with PregSense™ in pregnant women with singleton pregnancy > 32 + 0 weeks of gestation.
- All adverse events and serious adverse events related and unrelated to PregSense use.

As collected via PregSense™ and the data collected via the standard of care monitoring system (i.e. CTG).

Secondary Performance Endpoints:

- Uterine contractions

As collected via PregSense™ and the data collected via the standard of care monitoring system (i.e. CTG).

LIST OF ABBREVIATIONS

ACOG - American College of Obstetricians and Gynecologists
ADR – Adverse Device Reaction
AE – Adverse Event
APP - Proprietary Mobile Application
BMI – Body Mass Index
BT- Bluetooth
CCM - Cloud Computing Module
CE - European Conformity
CL – Cervical Length
CRC – Clinical Research Coordinator
CRF – Case Report Form
CTG – Cardiotocography
DPE - Data Processing Engine

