External monitoring is also done for a contraction stress test (CST), which records changes of the fetal heart rate during uterine contractions. It is performed near the end of pregnancy to determine how well the fetus will cope with the contractions of childbirth. The aim is to induce contractions and monitor the fetus to check for heart rate abnormalities using a cardiotocograph. A CST is one type of antenatal fetal surveillance technique. It may help predict the fetal capability to tolerate the stress of labor and vaginal delivery⁷.

The biggest advantage of Cardiotocography (CTG) is that it is an external device. The disadvantage is its inability to give an accurate reading on intrauterine pressure and activity. Without intrauterine pressure capability the CTG is not an indicated device for augmentation of labor. The CTG's readings can not only be influenced by intra-amniotic pressure but by local uterine muscle tension and abdominal wall flexing, etc. It is hampered by the thickness of the abdominal wall, which is why there is a high rate of failure in high BMI Moms.

Overall, in high BMI moms the accuracy in CTG is poor. Furthermore, the best position for CTG is supine, which is not desirable for the subject and limits mobility. The technology has remained essentially unchanged since 1968.

Internal monitoring: "Intrauterine pressure catheters (IUPC) and fetal scalp electrodes (FSE) are commonly used devices for intrapartum monitoring and management. Although the internal monitors used are sterilely packaged, they travel through the vaginal canal into the uterine cavity, providing a potential pathway for contamination and ascending infections⁸.

Internal monitoring can be done only after the cervix has dilated to at least 2 centimeters (cm) and the amniotic sac has ruptured and if the ECG cannot be performed as part of the routine gold standard.

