9.5.1 Performance Analysis Set (PA)

Because each monitoring modality sometimes fails to generate clinically interpretable data, rules were applied to facilitate statistical analysis.

The performance analysis set will consist of all subjects who finished the study without major protocol violations and had at least 1 minute of data where a signal was recorded and detected with both devices at the same time. Possible reasons for exclusion of a data point from this analysis set may include but are not limited to the following:

Invalid signal in one of the systems, i.e PregSense™ and the CTG system due to:

1. Device malfunction
2. Maternal movement
3. Device positioning does not enable signal recording
4. Interaction between devices

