9.6.3 Disposition of subjects

Subject disposition will be tabulated; the number of enrolled, exposed to study device, prematurely terminated and completed as planned subjects will be summarized, including the number of subjects in each analysis population. Device tolerability and compliance will be presented, the number and percent of subjects who fail to complete the study and the number and percent of subjects who fail to complete the study because of adverse events will be presented. A list of discontinued subjects, protocol deviations, and subjects excluded from the performance analyses will also be provided.

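### Completion is labelled subject compliance but depends on signal from both devices and on no protocol violation, so signal failures and minor deviations enter the tolerability and compliance figure

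*Combined protocol and SAP*

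**What the plan says.** The Study Synopsis lists among the safety endpoints "Safety, tolerability and compliance with PregSense™ in pregnant women with singleton pregnancy" beyond 32 weeks.

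Section 9.6.3 is the only place that says how tolerability and compliance are to be shown: "Device tolerability and compliance will be presented, the number and percent of subjects who fail to complete the study", followed by a second count, in which "subjects who fail to complete the study because of adverse events will be presented". The same section tabulates subjects enrolled, exposed, prematurely terminated and completed as planned, and the size of each analysis population. It also promises listings of discontinued subjects, protocol deviations and exclusions from the performance analyses.

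Section 7.5 defines the term on which that percentage rests: "Completion of study will be defined by the subject compliance, thus, subjects who finished the study without protocol violations and had at least 1 minute", continuing "of data where a signal was recorded and detected with both devices at the same time".

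Section 9.5.1 sets almost the same condition for the performance set, but excludes only major protocol violations. It explains: "Because each monitoring modality sometimes fails to generate clinically interpretable data, rules were applied to facilitate statistical analysis".

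**The concern.** Whether a minute of signal is detected on both devices at once is largely outside the woman's control. Most of the reasons for an invalid signal listed in 9.5.1 (device malfunction, positioning, interaction between the devices) are not subject behaviour; maternal movement is the exception. A minor deviation may also be the site's doing. Because 7.5 equates these conditions with subject compliance and 9.6.3 carries the result into the tolerability and compliance report, the overall percentage does not measure whether women tolerate the belt and follow the procedures. It combines subject-driven stops, test-device failure, reference-device failure and deviations. At stake is whether a safety endpoint named in the synopsis can be read from the table planned for it.

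**Working it through.** The plan states no figure for this point, so there is none to reproduce. The check sets the sections against each other and adds an illustration.

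**Text check**

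1. *Definition (7.5).* Complete = finished, and no protocol violation of any kind, and at least 1 minute detected on both devices. Failing any one condition makes a subject a non-completer.
2. *Use (9.6.3).* Tolerability and compliance are reported through the percent of non-completers and the subset due to adverse events. No other definition of either term appears in the documents.
3. *Session flow (5.1.2).* PregSense must pass a 2-minute validation before the 10-minute session, and a subject is excluded after three unsuccessful adjustments. The 30-minute paired session starts only once a valid CTG signal is found. A woman whose CTG gives no fetal heart rate therefore never starts the paired session, has no paired minute and is a non-completer by 7.5, although she did everything asked of her.
4. *Minor deviation.* A woman with paired data and one minor violation fails 7.5 but passes 9.5.1. The 9.6.3 table then counts her in the performance population but not among those who completed as planned.
5. *Traceability.* Section 5.2.1 requires withdrawal reasons in the CRF, but its list has no entry for signal failure. Section 9.6.3 gives listings and no summary by device or cause.

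**Illustration under assumed failure rates**

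Inputs: n = 50 (minimum recruitment, 9.4) and n = 200 (upper enrollment, Synopsis). Let a and b be the assumed shares of women with no usable PregSense or CTG signal, independent of each other. All women are fully cooperative and have no deviations. Women excluded at PregSense validation are counted as non-completers, which the plan leaves open.

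Non-completion rate f = 1 − (1 − a)(1 − b); expected number = n × f; P(at least one) = 1 − (1 − f)^n.

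| a, b | f | expected, n = 50 | P(at least one), n = 50 | expected, n = 200 |
|---|---|---|---|---|
| 0%, 5% | 5.0% | 2.5 | 0.92 | 10.0 |
| 2%, 2% | 1 − 0.98² = 3.96% | 1.98 | 0.87 | 7.9 |
| 5%, 5% | 1 − 0.95² = 9.75% | 4.9 | 0.99 | 19.5 |
| 10%, 10% | 1 − 0.90² = 19% | 9.5 | 1.00 | 38 |

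If completion instead meant undergoing every procedure the protocol allowed to start, non-completion would be 0% in every row.

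**The case against.** The strongest reply is that little depends on this figure and that the plan already separates much of what is mixed.

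- *Stakes.* Tolerability and compliance appear as an endpoint only in the synopsis. Sections 4.2 and 9.2.2 define the safety endpoint as adverse event incidence, and 9.6.4.3 makes that incidence the primary safety variable. The success criterion in 9.3 does not use completion. All of this stands and limits the point to a descriptive safety and disposition measure.
- *Separation.* The adverse-event subset, the count closest to tolerability, is untouched by signal failure. A reader might infer that the plan conceals PregSense failure. The documents do not support that: 8.3 has technical failures recorded in the CRF, section 14 has malfunctions reported within 24 hours, and 9.6.3 gives analysis-set counts and exclusion listings. What is missing is a summary by device and cause, so the listings give only partial tracing.
- *Who is affected.* A reader might picture a woman who wears the belt through both sessions while the CTG detects nothing. Section 5.1.2 rules this out, because the paired session would not start. The misclassified women are those stopped at a signal check, those whose paired session yields no joint minute, and those with a minor deviation. Since 7.5 says only a signal, and 7.2.2 takes maternal heart rate from a pulse oximeter, one joint maternal minute might be enough once the session runs, which would reduce the count.
- *PregSense exclusions.* It is unstated whether women excluded after three failed adjustments count as non-completers, so PregSense failures may inflate the figure or drop out of it. That is a further ambiguity to settle, and not a defence.
- *Body mass index.* A reader might use the Background remark on CTG, "which is why there is a high rate of failure in high BMI Moms", to predict many failures in heavier women. It follows sentences about intrauterine pressure, uterine muscle tension and the abdominal wall, and does not clearly concern loss of the fetal heart rate signal. Section 9.5.1 is the sounder support.

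It could also be argued that 9.6.3 lists tolerability and compliance apart from the two counts that follow. Even so, the only definition on offer is the one in 7.5, which ties compliance to completion.

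**Conclusion.** The point holds as a wrong rule and not merely a missing detail. Followed as written, 7.5 and 9.6.3 place cooperative women with no paired signal, and women with minor deviations, in the overall tolerability and compliance percentage. The violation rules in 7.5 and 9.5.1 also conflict within one disposition table.

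The size cannot be determined. The 4% to 19% range for failure rates of 2% to 10% on both devices rests wholly on assumed, independent rates and on counting validation exclusions as non-completers; it should not be read as a forecast. Minor deviations would add to it. The adverse-event subset, the adverse event analysis, the sample size and the limits-of-agreement result are not affected. A reader might infer that the primary conclusion is in doubt on this ground, and the documents give no basis for that.

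**What to change.** - *7.5:* define completion as having undergone every study procedure and session that the protocol allowed to start under 5.1.2, regardless of signal yield or minor deviations. Requiring the belt to be worn through both the 10-minute and 30-minute sessions would not work, because women stopped at a signal check would still be non-completers.
- *9.6.3:* report tolerability and compliance from subject-driven stops and from adverse events. Add separate rows for (i) failed PregSense validation or no PregSense signal, (ii) no CTG signal and (iii) no paired minute. State that women excluded after three failed adjustments are counted in row (i).
- *9.5.1:* keep the 1-minute paired rule and the major-violations rule here only.

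The cost is revised wording in two sections and three table rows from data already being recorded, with no new procedures. The only drawback is a slightly longer disposition table.
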